#### **4.2 Secondary and Exploratory Outcome Variables**

A separate analysis will be conducted to determine which post-covid symptom(s) are more impacted by omega-3 supplement. The Bi-weekly Symptoms and Quality of Life Post Covid-19 Survey (Appendix C) includes the four symptoms being measured (respiratory, fatigue, lack of taste, lack of smell). Therefore, this bi-weekly survey will be used for this efficacy analysis.

#### **5.0 Study Intervention / Investigational Agent**

The investigational product is EPA+DHA, an omega-3 supplement manufactured by KD Pharma.

### **6.0 Procedures Involved**

#### **6.1 Study Design**

This is a double-blind, randomized controlled trial (RCT) with two treatment arms:

Arm 1 - Omega-3 (EPA+DHA) – Dose is 2,100mg per day via 3 mini-capsules, 2x/day (a total of 6 mini-capsules per day). Each capsule has 252mg of EPA and 102mg of DHA.

Support for dosing:

- The American Heart Association (AHA) says taking up to 3 grams of fish oil daily in supplement form is considered safe [33]
- Up to 5,000mg of omega-3 fatty acids per day is considered safe [34].
- The U.S. Food and Drug Administration recommends consuming no more than 3 g/day of EPA and DHA combined, including up to 2 g/day from dietary supplements.[35]

Arm 2 - Placebo – made from soybean oil (same dosing schedule as intervention arm)

Supplement and placebo will be supplied by KD Pharma.

#### **6.2 Research Procedures**

For an overview of the study, please see figure 1 below.

1. Team members who email the study team at the address on the flyer will be sent an eligibility survey in REDCap to determine if study inclusion criteria are met.
2. Those who meet study inclusion criteria will then be sent the study consent form in REDCap, and encouraged to call or email the study team with questions.

3. If the patient expresses further interest in study participation, s/he will be consented via REDCap and then will be sent a link to the baseline survey in REDCap.
4. Upon consent, RC will assign ID# and enter the subject into REDCap (study data management system).
5. Subjects will be randomly assigned to receive 3 Omega-3 (EPA+DHA) mini-capsules twice daily (total of 2,100mg per day) for 12 weeks in the experimental intervention arm or three placebo mini-capsules twice daily for 12 weeks.
  - Study supplement or placebo are supplied at no cost to the subject and will be mailed to the subject's home.
  - Study subjects will receive two shipments over the course of study participation.
    - Package 1 upon enrollment
    - Package 2 at the end of week 4
  - Subjects will also receive, in these shipments, two spot blood sample tests for omega-3 levels, and directions indicating when to use the test kits.
6. All study subjects in each arm will be asked to give a spot sample (2 drops) of blood at baseline and again after 12 weeks (end of study participation). This will be done using OmegaQuant test kits that are mailed to the subject's home. The de-identified samples will be mailed by the subject in the provided envelope to OmegaQuant Lab, associated with University of South Dakota Medical Center, for analysis of omega-3 levels. These tests involve no cost to the subject. Subjects will be informed of their omega-3 level after results are returned from the lab and the subject's participation in the study is complete.
7. Monitoring of Subjects:
  - Subjects will be encouraged to call RC at any time with study questions. RC will also call each subject weekly to ensure procedures are being followed and answer any questions. The weekly "check-in call" will occur for 12 weeks.
  - Each subject will be checking their blood pressure. Subjects will report their blood pressure via REDCap in their bi-weekly survey. Reported adverse events will be documented.
  - Subjects in both arms will be tracked for 3 months (12 weeks). An interim analysis will be done for a sub-sample (the first 20 subjects) after three weeks of participation to determine if any arm should be adjusted or terminated.
  - Participants will continue to receive standard of care and follow up for any routine conditions being managed at HackensackUMC.
8. The final study activity will include the 2nd spot blood sample and a short survey (survey link emailed to subject via REDCap) to collect feasibility and acceptability data. The survey will take about 10 minutes to complete.

9. Subjects will then be mailed a \$40 gift card for completing the study.

10. Subjects will be informed of their omega-3 level after results are returned from the lab and the subject's participation in the study is complete

Any subject missing both daily doses 3 times a week for 3 weeks in a row will be removed from the study for non-compliance, and asked to dispose of any unused study supplement/placebo. This will be documented in a dedicated RedCap survey for anyone who discontinues study participation, either for non-compliance or of their own will.

Any subject who has another covid-19 infection during study participation may continue on the study. The RC will inform the subject of this if/when any subject reports a new covid infection.

[figure not shown]

Figure 1: Study Schema

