## **4.0 Study Endpoints**

### **4.1 Primary Outcome Variables**

The primary endpoint is evaluation of feasibility and acceptability of omega-3

supplementation v. placebo to limit post-covid syndrome among adult patients. The Follow-up Feasibility Survey (Appendix D) will be used for this analysis.

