#### **14.0 Withdrawal of Subjects**

If a subject needs to be withdrawn from the study without their consent for medical reasons or non-compliance, she or he will be notified by [name] or [name] by phone, with a follow-up letter mailed to the subject's home.

If a subject chooses to withdraw from the study, she or he must notify the PI by calling the phone number on the consent form. All data collected up to the point of termination will be kept in the study.

Any subject missing both daily doses 3 times a week for 3 weeks in a row will be removed from the study for non-compliance, and asked to dispose of any unused study supplement/placebo.

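### The missed-dose rule removes subjects from the study, not only from capsules, so on the plain reading their later symptom surveys and week-12 blood spot are lost

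*Combined protocol and SAP*

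**What the plan says.** Section 6.2 sets the rule: "Any subject missing both daily doses 3 times a week for 3 weeks in a row will be removed from the study for non-compliance". Section 14.0 repeats it in the same words.

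Two further sentences show that the rule ends participation and not merely dosing. Section 6.2 provides a dedicated REDCap survey "for anyone who discontinues study participation, either for non-compliance or of their own will", which puts non-compliance alongside voluntary withdrawal. Section 14.0 treats it as grounds for involuntary withdrawal, in the sentence that begins "If a subject needs to be withdrawn from the study without their consent for medical reasons or non-compliance". On data already in hand, section 14.0 says "All data collected up to the point of termination will be kept in the study"; that sentence follows the one on voluntary withdrawal.

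The outcomes concerned are these:

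- Symptoms come from Appendix C. Section 4.2 says "this bi-weekly survey will be used for this efficacy analysis".
- Omega-3 level comes from a blood spot at baseline and a second at 12 weeks (section 6.2).
- Feasibility and acceptability come from Appendix D. Section 4.1 says "The Follow-up Feasibility Survey (Appendix D) will be used for this analysis".
- Section 17.1 names the comparison of symptom recovery between arms as the primary analysis. It gives no analysis population and no rule for missing data.

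Two general sentences in section 6.2 point the other way: "All study subjects in each arm will be asked to give a spot sample" and "Subjects in both arms will be tracked for 3 months (12 weeks".

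**The concern.** Stopping study capsules and leaving the study are different events, and the plan merges them. A subject who stops capsules can still report symptoms and give a blood spot. A subject removed from the study is no longer due for either.

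The subjects lost this way are selected after randomisation by their adherence, which treatment may affect: section 15.0 lists diarrhea and reflux symptoms as risks of omega-3. If removals differ between arms in how many there are or in how those subjects would have fared, comparing the subjects who remain is no longer a comparison of the randomised groups. Recruiting beyond 100 replaces numbers but does not recover the missing outcomes.

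Acceptability may also be affected. Appendix D asks about skipped doses, ease of taking the pills and satisfaction, and people who stopped taking six capsules a day are well placed to answer. This harm is only possible, because the plan does not make clear whether they receive the survey.

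**Working it through.** **Does anything restore follow-up after removal?**

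- The general sentences on blood spots and 12-week tracking (section 6.2) do not mention removed subjects. They sit beside a specific rule that takes those subjects out.
- The Study Discontinuation Verification form in Appendix D has three items: whether participation has ended, the pill count and whether pills were discarded. None concerns symptoms.
- Section 19.1.2 continues adverse-event monitoring for at least 30 days after the last dose. This covers safety only.
- Section 19.3 describes a phone survey at 6 months. Its content is not specified, and it falls after week 12.
- For Appendix D, section 1.0 places the feasibility survey at the end of a subject's participation, which could include removed subjects. Section 6.2 makes it part of the final study activity with the second blood spot, which suggests it does not.

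None of these supplies the later Appendix C surveys or the week-12 spot.

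**How demanding is the threshold?** Three days a week for three weeks is 3 × 3 = 9 of 21 days. At six capsules a day that is 9 × 6 = 54 of 21 × 6 = 126 capsules, or 43%. A subject just at the threshold may still have taken 57% of capsules in those weeks, so their outcomes are informative.

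**What is lost, by time of removal?** Section 1.0 gives a survey every two weeks for 12 weeks. Assume weeks 2, 4, 6, 8, 10 and 12. Surveys lost are those due after removal:

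- end of week 3 (earliest possible): 5 of 6
- week 4 or 5: 4
- week 6 or 7: 3
- week 8 or 9: 2
- week 10 or 11: 1

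Every removal before week 12 therefore loses the week-12 survey and the week-12 spot.

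**What figure does the plan give?** Sections 1.0 and 12.0 give 100 subjects for analysis and up to 120 recruited, depending on attrition: 120 − 100 = 20, and 20/120 = 16.7%. This limits recruitment. It is neither a forecast of removals nor a cap on attrition.

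**How large could the effect be?** These are illustrations with assumed inputs, not estimates.

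- If 10 of 60 outcomes were missing in each arm, worst-to-best-case bounds on the risk difference would be 10/60 + 10/60 = 33 percentage points wide.
- Take no true effect, 60 per arm and 40% recovery in both. Remove 10 on omega-3, none of whom recover, and nobody on placebo. Those remaining show 24/50 = 48% against 24/60 = 40%, a spurious 8 points. The approximate two-sided rejection rate is 0.135 instead of 0.05.
- Take 20% recovery, 10 removed on omega-3 and 4 on placebo, with removed subjects recovering at 10%. The result is (12 − 1)/50 = 22.0% against (12 − 0.4)/56 = 20.7%, or 1.3 points, with a rejection rate of about 0.053.
- Equal removal of similar subjects gives no bias.
- Equal numbers with different prognosis can still give bias. With 40% recovery and 10 removed per arm, suppose none of the omega-3 removals recover but 4 of 10 placebo removals do. The result is 24/50 = 48% against (24 − 4)/50 = 40%.

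**The case against.** The strongest reply is that non-collection is inferred. No sentence says the surveys or the spot stop. Section 7.1 says each subject will have two specimens. Section 19.3 lists what ends follow-up (death, 6 months after the last dose, loss to follow-up or withdrawn consent), and removal for non-compliance is not on the list. The study schema is also not reproduced in the text available. This stands in part: a reader might infer that the plan expressly ends all follow-up, and it does not. But the specific rule, its classification as ending participation and the three-item form all point one way, and the contacts that remain do not collect the outcomes in question.

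The size is also unknown. The threshold is high, weekly calls and a $40 completion card support adherence, both arms take six oil capsules a day, and section 15.0 softens gastrointestinal effects with food and split doses. Removals may be few and balanced. That stands. A reader might take the 8-point illustration, or the 20-subject allowance, as an expected or maximum effect. The documents support neither.

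A further point concerns the value of the lost forms. Appendix C's choices for when a symptom stopped end at the fourth week after diagnosis, while section 10.0 requires symptoms for more than 12 weeks. This is a separate weakness and limits what the extra surveys would recover. The form still has a choice for symptoms that persist and a fatigue rating, and the blood spot is unaffected.

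Finally, the trial is a feasibility study and section 17.1 says it is not powered. Section 17.1 nevertheless tests symptom recovery as the primary analysis at p ≤ 0.05, and section 2.0 intends the trial as proof of concept for a larger one.

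**Conclusion.** The concern holds as a design choice that should be changed. As written, the rule plausibly loses adherence-related outcomes after randomisation: at least the week-12 survey and blood spot for any removal before week 12, and up to 5 of 6 surveys, on the assumed schedule. This can bias the comparison of symptom recovery if removals differ between arms in number or prognosis. The documents do not establish that it will, or by how much.

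A reader might also infer that reported acceptability will be inflated. That is not shown, because it is unclear whether removed subjects answer Appendix D. Removals can in any case be counted by arm, and earlier data appear to be kept. The gap is in later outcomes, and possibly in acceptability, not in the number removed.

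**What to change.** - **Sections 6.2 and 14.0:** state that subjects who meet the missed-dose rule may be told to stop capsules but stay in the study. Bi-weekly surveys, weekly calls, the week-12 spot and Appendix D continue unless the subject withdraws consent or a study physician ends participation for medical reasons.
- **Section 14.0:** delete non-compliance from the sentence on withdrawal without consent. Medical withdrawal stays.
- **Discontinuation form:** record stopping capsules separately from ending participation.
- **Section 17.1:** state that all randomised subjects are analysed in their assigned arm, and that non-compliance is reported by arm as a feasibility result.

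The cost is a short amendment with IRB approval (section 20.1). Surveys, calls and two blood kits per subject are already planned. Section 6.2 does not say which shipment carries the second kit. If it is Package 2, sent at the end of week 4, a subject stopped at the end of week 3 would need it mailed separately. Gift cards for retained subjects would add $40 each, for example 20 × $40 = $800 for 20 subjects, which is not a maximum. Some of these subjects may not keep responding, and reported adherence and acceptability may look less favourable.

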## 1.0 Study Summary

Study Title	HMH Omega-3 Covid Recovery Study
Study Design	We will conduct a two-arm, double blind randomized 12-week study to supplement omega-3 (EPA + DHA) among 100 adults (age 18+) who had covid-19 and are experiencing possible after-effects from the illness (post-acute sequelae of covid-19, also called post-covid syndrome or long covid syndrome).
Primary Objective	The primary objective is to serve as a feasibility study for omega-3 fatty acid supplementation v. placebo in adult patients to limit long covid syndrome. This will serve as a proof-of-concept for a larger follow-up study to subsequently be conducted.
Secondary Objective(s)	Determine which of the post-covid symptom(s) are most impacted by omega-3 supplement.
Research Intervention(s)/Investigational Agent(s)	Participants will be assigned to one of two study arms and asked to take an Omega-3 supplement or placebo for 12 weeks. Participants will report symptoms bi-weekly throughout the study period. A spot blood sample to assess omega-3 levels will be done at baseline and at the end of the 12-week study period.  A survey will be used bi-weekly to assess health status and outcomes via patient self-report. Data on demographics and comorbidities such as obesity and diabetes will be collected at baseline. At the end of study participation, subjects will take a follow-up survey assessing feasibility.
IND/IDE #	IND # 157250
Study Population	Hackensack Meridian Health team members age 18+ who tested positive for COVID-19 28+ days prior and who are not already taking an Omega-3 supplement.
Sample Size	50 participants in each arm = 100 total for final analysis (up to 60 participants in each arm will be recruited if needed, dependent on attrition for a total of up to 120)
Study Duration for individual participants	Individual participants will be in the study for 12 weeks. During the 12 week study period, subjects will be sent a survey every two weeks. At the end of the 12 weeks, subjects will complete a short survey collecting feasibility and acceptability data.
Study Specific Abbreviations/Definitions	
 
• Hackensack Meridian Health (HMH)
 
• Center for Healthy Senior Living (CHSL)
 

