## **8.0 Sharing of Results with Subjects**

Individual-level data (the results of both COVID-19 tests and the omega-3 levels from the blood draw if applicable) will be shared with participants. The major findings of the study and aggregate data, will be shared with participants after the study has concluded.

1) Unblinding will occur when a subject drops out of the study due to an adverse event. The subject will be informed of their study arm assignment via email so that they can better understand any possible adverse reaction to the study medication.

2) Subjects who complete the study will be unblinded and informed of their study arm assignment via email after the study team has seen their data (descriptive statistics generated by RedCap). This will be done within 4 weeks of each subject finishing the study.

The study coordinator will inform each subject when they finish study participation, to expect an email advising which study arm they were in.

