## **12.0 Local Number of Subjects**

The number of subjects will be 50 in each of two arms, for a total of 100 subjects for analysis. Up to 60 participants in each arm will be recruited if needed, dependent on attrition, for a total of up to 120 subjects.

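### The survey behind the primary feasibility endpoint is placed at week 12, early leavers are documented on a form with no acceptability items, and no denominator is named, so acceptability probably rests on those who stayed

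*Combined protocol and SAP*

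**What the plan says.** **The endpoint and its source.** Section 4.1 makes feasibility and acceptability the primary endpoint and names one source: "The Follow-up Feasibility Survey (Appendix D) will be used for this analysis".

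**When the survey is given.** Section 1.0 has two lines. One reads "At the end of the 12 weeks, subjects will complete a short survey collecting feasibility and acceptability data". The other reads "At the end of study participation, subjects will take a follow-up survey assessing feasibility". In section 6.2, step 8 makes the last study activity the second blood spot plus "a short survey (survey link emailed to subject via REDCap) to collect feasibility and acceptability data". Step 6 of the same section times that second spot at 12 weeks and treats this as the end of participation.

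**What leavers receive.** Section 6.2 provides for removal for sustained missed doses and then says: "This will be documented in a dedicated RedCap survey for anyone who discontinues study participation, either for non-compliance or of their own will". The Study Discontinuation Verification form in Appendix D asks three things: whether the subject has stopped, how many pills are left, and whether they have been discarded. Questions on ease, interference with daily life and satisfaction appear only on the Follow-up Survey.

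**Other information on leavers.** Section 14.0 says: "All data collected up to the point of termination will be kept in the study". Section 17.3 stores notes from the weekly calls. Section 19.3 plans a telephone survey at 6 months. Section 8.0 says: "Unblinding will occur when a subject drops out of the study due to an adverse event".

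**Numbers and analysis set.** The target is 100 subjects for analysis. Section 12.0 adds: "Up to 60 participants in each arm will be recruited if needed, dependent on attrition", for at most 120. Section 17.1 summarises data overall and by arm but defines no analysis set, denominator or missing-data rule.

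**The concern.** Section 16.0 says the study is to show whether a larger trial is warranted. For that decision, the views of people who stopped matter at least as much as the views of those who finished. If the acceptability questions reach only subjects still present at week 12, the result describes the stayers.

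The loss is unlikely to be random. Subjects with sustained missed doses are removed before the adherence and satisfaction questions are asked. If leavers are less favourable than stayers, the reported figure is optimistic, and no item common to both groups would reveal it. If leaving differs by arm, a comparison among week-12 respondents is no longer the full randomised comparison.

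Counts of removals and withdrawals will exist, so retention can be computed. The gap lies in acceptability, in the lack of a common adherence measure (the only pill-count item is on the discontinuation form), and in the unnamed denominator.

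**Working it through.** **Step 1: who gets the survey.**
- Section 4.1 names the Follow-up Feasibility Survey and nothing else.
- One line of section 1.0 and step 8 of section 6.2 put it at week 12. The other line of section 1.0 ties it to the end of participation, a phrase that section 6.2 elsewhere equates with 12 weeks.
- The survey's own adherence question looks back over the whole 12-week study, which suits finishers.
- Leavers are directed to a different form with no acceptability item.
- No text in sections 6.2, 14.0 or Appendix D sends leavers the feasibility survey. Figure 1 could not be checked.

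The week-12 reading is therefore the likelier one, but not certain.

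**Step 2: the plan's own counts.** 2 × 50 = 100 for analysis; 2 × 60 = 120 at the ceiling. No attrition rate is stated, so 120 cannot be derived from an input. Solving backwards, 1 − 100/120 = 16.7% attrition gives 120. So does adding 20% (100 × 1.20 = 120), whereas dividing by 1 − 0.20 gives 125.

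**Step 3: how far the survey could leave the answer open.** Suppose recruitment reaches 120 and exactly 100 answer. Let r be the favourable share among the 100 and d the share among the other 20. Both are assumed; the protocol defines no favourable rate.

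Share of all randomised = (100r + 20d)/120.

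| Assumed r | d = 0 | d = 1 |
|---|---|---|
| 70% | 70/120 = 58.3% | 90/120 = 75.0% |
| 80% | 80/120 = 66.7% | 100/120 = 83.3% |
| 90% | 90/120 = 75.0% | 110/120 = 91.7% |

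The width is (100r + 20)/120 − 100r/120 = 20/120 = 16.7 points, whatever r is. If leavers feel as stayers do (d = r = 90%), the share is 108/120 = 90.0% and there is no bias.

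**Step 4: other amounts of missing response.** With r assumed at 80% and 120 randomised, the bounds are 76–81% if 5% are missing, 72–82% if 10% are missing and 60–85% if 25% are missing. With no attrition and full response the width is 0.

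**Step 5: unequal loss by arm.** Assume 55 and 45 respondents of 60 per arm, with 80% favourable among respondents in each. The respondent comparison shows 0 difference. Counting non-respondents as unfavourable gives 44/60 = 73.3% and 36/60 = 60.0%, a difference of 13.3 points.

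**The case against.** **The text does not exclude leavers.** The line "At the end of study participation, subjects will take a follow-up survey assessing feasibility" can be read to cover anyone whose participation ends, at whatever week. Appendix D holds both forms under one title, and nothing says that the discontinuation form replaces the survey. This stands in part: it makes the routing gap a likely reading rather than a stated rule. It does not close the gap, because no visible procedure puts the wider reading into effect.

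**Other data on leavers exist.** Data up to termination are kept, call notes are stored and a 6-month call is planned. However, section 4.1 names none of these as a source for the primary endpoint. The call notes have no stated acceptability items, and the content of the 6-month call is not given. That call would also come after unblinding for adverse-event leavers and for finishers, whom section 8.0 unblinds within 4 weeks of finishing.

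**The 20 of 120 is a recruitment ceiling.** This stands. A reader might infer that the plan prescribes a completers-only analysis, or that 20 subjects will be excluded. The documents say neither. One hundred is a target, 120 applies only if needed, data up to termination are kept, and section 17.1 speaks of all study data. The width in Step 3 shows what could be left open; it does not estimate bias.

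**It is an unpowered feasibility study with no feasibility threshold.** That is so, and no stated decision can be shown to flip. But acceptability is the primary endpoint here, so who answers the survey is central.

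**A wider remedy would overreach.** One might want to continue the bi-weekly surveys in removed subjects. Sections 6.2 and 14.0 remove such subjects from the study, so that would change what removal means. It is not proposed.

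**Conclusion.** The point holds with medium confidence and should be fixed. On the likelier reading, the primary acceptability result comes from those still present at week 12, after subjects with sustained missed doses have been removed, and section 17.1 does not say over whom it is reported. The result is optimistic if leavers are less favourable, and unbiased if they are not.

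At the plan's own recruitment ceiling, with 100 responses, the all-randomised share would be undetermined by 16.7 points. Fewer responses would widen this, and full retention and response would bring it to 0. All favourable rates, and the split by arm, are assumptions. The documents do not support saying that leavers are certainly denied the survey; Figure 1 should be checked. The removal rule itself is not judged here.

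**What to change.** 1. **Send the survey to everyone.** State in section 6.2 that the Follow-up Feasibility Survey goes to every randomised subject at week 12 or at discontinuation, whichever comes first, as far as consent allows. Reword its adherence question to refer to the subject's time in the study rather than to 12 weeks. Send the link when the subject discontinues, without delaying the adverse-event unblinding message in section 8.0, and record whether the answer came before or after unblinding.
2. **Name the denominator in section 17.1.** Report retention and removal by assigned arm over all randomised subjects. Report acceptability among respondents with the number of non-respondents by arm, and add a bound that counts non-respondents as unfavourable.
3. **Optional.** Ask everyone for the remaining pill count, interpreted against the recorded number of capsules dispensed and days on study. Section 6.2 describes two shipments without quantities, so a leftover count alone does not measure adherence.

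**Cost.** An IRB-approved amendment (section 20.1), a change to REDCap routing, one reworded item and some reminders. Answers given after unblinding would need to be read separately, and the acceptability figure may come out less favourable.
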